13.4 Time Period and Frequency for Event Assessment**13.4.1. AE/SAE Monitoring**

Each enrolled subject will be monitored for the occurrence of AEs, including SAEs, beginning immediately after FMT. The occurrence of an adverse event (AE) or serious adverse event (SAE) may come to the attention of study personnel during study visits and interviews of a study participant presenting for medical care, or upon review by a study monitor. Subjects will be questioned at each follow up time-point about unsolicited and solicited AE on stool form and frequency, presence of abdominal pain, fevers and subjective well-being and/or examined (at day

1, 2, 6, 10 and 12 weeks post-FMT via phone call; 4 and 8 weeks post-FMT via office visit and review of patient diary for AE monitoring) by the treating physician for evidence of AEs. The questioning of subjects with regard to unsolicited adverse events will be generalized such as, "How have you been feeling since your last visit?". The following AEs will be solicited via phone calls and clinic visits by a study coordinator, along with the intensity of each:

1. Fever
 - a. Mild: Temperature 37.7-38.6°C
 - b. Moderate: Temperature 38.7-39.3°C
 - c. Severe: Temperature 39.4-40.5°C
 - d. Potentially Life Threatening: Temperature >40.5°C
2. Chills
 - a. Mild: No or minimal interference with usual social and functional activities
 - b. Moderate: Greater than minimal interference with usual social and functional activities
 - c. Severe: Inability to perform usual social and functional activities
3. Fatigue/Malaise
 - a. Mild: No or minimal interference with usual social and functional activities
 - b. Moderate: Greater than minimal interference with usual social and functional activities
 - c. Severe: Inability to perform usual social and functional activities
 - d. Potentially Life Threatening: Incapacitating fatigue or malaise symptoms causing inability to perform basic self-care functions.
4. Anorexia (loss of appetite)
 - a. Mild: Loss of appetite without decreased oral intake
 - b. Moderate: Loss of appetite with decreased oral intake without significant weight loss
 - c. Severe: Loss of appetite with decreased oral intake associated with significant weight loss
 - d. Potentially Life Threatening: Life threatening consequences or aggressive intervention indicated (TPN or tube feeding)
5. Abdominal Pain
 - a. Mild: Pain causing no or minimal interference with usual social and functional activities.

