7.1.2 Psyllium Husk Powder

All subjects assigned to the fiber treatment arms will be required to take 1 teaspoon (approximately 5 grams) of psyllium husk powder twice a day (morning and night) for 8 weeks, beginning 3 days prior to Week 0 screening colonoscopy. To simplify, enrolled participants will consume approximately 10g of psyllium per day for 59 days.

The FDA characterizes psyllium seed husk as the dried form of a psyllium seed coat³³.

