12.6 Reporting and Exclusions

12.6.1 Evaluation of Toxicity

All subjects will be evaluable for toxicity from the time of their first treatment with FMP250.

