- AEs, actions taken as a result of AEs, and follow-up results must be recorded in the patient's medical record.
- In addition, patients will receive a follow up phone call 6-months post FMT and every subsequent 6 months for the next year to record any SAEs, new medical conditions and diagnoses, or changes in conditions or diagnoses since last study contact.

For all SAEs and AEs, relevant clinical assessments and laboratory tests will be repeated as clinically appropriate, until final resolution or stabilization of the event(s).

All AEs including local and systemic reactions not meeting the criteria for SAEs will be captured on the appropriate electronic case report form (eCRF). Information to be collected includes event description, time of onset, clinician's assessment of severity, relationship to study product (assessed only by those with the training and authority to make a diagnosis), and time of resolution/stabilization of the event. All AEs occurring while on study must be documented appropriately regardless of relationship. All AEs will be followed to adequate resolution.

Any medical condition that is present at the time that the participant is screened will be considered as baseline and not reported as an AE. However, if the study participant's condition deteriorates at any time during the study, it will be recorded as an AE.

Changes in the severity of an AE will be documented to allow an assessment of the duration of the event at each level of severity to be performed. AEs characterized as intermittent require documentation of onset and duration of each episode.

Study coordinators will record all reportable events with start dates occurring any time after informed consent is obtained until 7 (for non-serious AEs) or 30 days (for SAEs) after the last day of study participation. At each study visit, the investigator will inquire about the occurrence of AE/SAEs since the last visit. Events will be followed for outcome information until resolution or stabilization.

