13.4.2.2 Assessment of Causality

The physician must assess the relationship of any AE (including SAEs) to FMT, as related or not related, based on clinical judgment and using all available information, and may include consideration of the following factors:

- a. Possible alternative causes of the AE, including the disease under treatment, pre-existing conditions, concomitant use of other drugs, and presence of environmental or genetic factors.
- b. The temporal association between FMT exposure and onset of the AE.
- c. Whether the manifestations of the AE are consistent with known actions or theoretical toxicity of FMT.

The causal relationship between FMT and the AE will be assessed using one of the following categories:

- a. Not Related: An AE is not associated with FMT if:
 - An event that can be determined with certainty to have no relationship to the FMT.
 - Temporal relationship is lacking (i.e. the event did not occur within a reasonable time frame following administration of FMT)

[figure not shown]
- Other causative factors more likely explain the event (i.e. pre-existing condition, other concomitant treatments);
- b. Definitely Related:
 - There is a positive temporal relationship (i.e. the event occurred within a reasonable time frame following FMT)
 - The AE is more likely explained by FMT than by another cause
 - Previously known toxicity of FMT.
- c. Probably Related:
 - There is a positive temporal relationship (i.e. the event occurred within a reasonable time frame following FMT)
 - The AE is more likely explained by FMT than by another cause
 - Unlikely to be explained by patient's clinical state or other intervention.
- d. Possibly Related:
 - There is a positive temporal relationship (i.e. the event occurred within a reasonable time frame following FMT)
 - Event follows an expected response pattern to FMT, but event could have occurred secondary to a number of other factors.

14. Unanticipated Problems Involving Risks to Subjects or Others

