14.1.2 Unanticipated Problem Reporting

The sub-investigators will report unanticipated problems (UPIRTSOs) to the reviewing Institutional Review Board (IRB) and to the lead principal investigator (PI). The UPIRTSO report will include the following information:

- Protocol identifying information: protocol title and number, PI's name, and the IRB project number;
- A detailed description of the event, incident, experience, or outcome;
- An explanation of the basis for determining that the event, incident, experience, or outcome represents an UPIRTSO;
- A description of any changes to the protocol or other corrective actions that have been taken or are proposed in response to the UPIRTSO.

To satisfy the requirement for prompt reporting, UPIRTSOs will be reported using the following timeline:

- UPIRTSOs that are serious adverse events (SAEs) will be reported to the IRB within 1 week of the investigator becoming aware of the event.
- Any other UPIRTSO will be reported to the IRB within 2 weeks of the investigator becoming aware of the problem.
- All UPs should be reported to appropriate institutional officials (as required by an institution's written reporting procedures), the supporting agency head (or designee), Food and Drug Administration (FDA), and the Office for Human Research Protections (OHRP) within one month of the IRB's receipt of the report of the problem from the investigator.

15. Data and Safety Monitoring Plan (DSMP)

A Weill Cornell Medicine Data Safety Monitoring Board (WCM DSMB) will monitor the data collected in this clinical trial on a quarterly basis to ensure the safety of enrolled subjects. The first periodic report to the DSMB will be within 3 months after enrolling the first subject and will be submitted through the

following link: <https://research.weill.cornell.edu/integrity-compliance/research-support/human-research/data-safety-monitoringboard/make-submission>. This monitoring plan was chosen for this clinical trial because it will be randomized and is intended to provide definitive information on the effectiveness and safety of FMTs and fiber supplements in active UC patients.

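### The adverse-event start point, toxicity population and causality target are inconsistent across sections and do not properly cover psyllium

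*Combined protocol and SAP*

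**What the plan says.** **Start of AE recording.** Section 13.4.1 gives two starts. Its first sentence is "Each enrolled subject will be monitored for the occurrence of AEs, including SAEs, beginning immediately after FMT". A later paragraph reads "Study coordinators will record all reportable events with start dates occurring any time after informed consent is obtained", and the same section adds "All AEs occurring while on study must be documented appropriately regardless of relationship". Section 13.1 defines an AE as occurring in a person who has been given FMT, and Section 13.2 places SAEs during or after FMT.

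**Toxicity population.** Section 12.6.1: "All subjects will be evaluable for toxicity from the time of their first treatment with FMP250".

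**Psyllium.** Section 7.1.2 has subjects in the fiber groups take it for 59 days, "beginning 3 days prior to Week 0 screening colonoscopy". Sections 6.1.1 and 7.8.2 agree on that start. Randomization happens at the screening visit (Section 6.1.2), before the endoscopic eligibility check on day 0. Section 4.5 accepts that a screen failure may already have been randomized, and the only safety item in its minimum data set is SAEs.

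**Causality.** Section 13.4.2.2: "The physician must assess the relationship of any AE (including SAEs) to FMT". Section 13.1.11 grades attribution to the *study treatment*, and the case report form described in 13.4.1 takes relationship to the *study product*. Neither term is defined.

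**Aim.** Section 15 says the trial is meant to give "definitive information on the effectiveness and safety of FMTs and fiber supplements".

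**The concern.** Psyllium is a randomized intervention in this trial. It starts before FMT and has its own listed risks (choking and bloating in Sections 2.5.1.2 and 13.1.7). A safety plan that promises information on fiber should count events from first exposure to fiber, include everyone exposed, and let the assessor say that fiber was the cause. Three of the plan's rules are instead tied to FMT, and other passages disagree with them.

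The causality rule matters most because it applies to the whole course rather than to three days. Section 12.4.2 lists the number and type of treatment-related AEs as a safety measure. If relatedness means related to FMT, an event the physician ascribes to psyllium drops out of that count. Section 12.1 also plans a safety comparison of placebo FMT with fiber against placebo FMT alone. Before week 8 neither of those groups has received investigational FMT, so a judgement of relatedness to FMT says almost nothing about that contrast.

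**Working it through.** **1. Reproduce the plan's figure.** Three days before FMT plus 8 × 7 = 56 days gives 3 + 56 = 59, as stated in Section 7.1.2.

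**2. Subjects on psyllium.** All 45 in Group 2, plus half of the 45 in Group 3 (Section 3.1), which is 22 or 23. Total: 67 or 68 of 135. As a share, 1/3 + 1/2 × 1/3 = 1/2.

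**3. Exposure before FMT.** 3/59 = 5.1% of the course. In subject-days, 67 × 3 = 201 and 68 × 3 = 204. The remaining 56/59 = 94.9% follows FMT and is monitored under either start.

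**4. Psyllium-exposed subjects who fail on day 0.** Section 12.2 expects 15 screening failures or dropouts among 150 but does not say how many fail at the day-0 colonoscopy. Assuming 5, 10 or 15 such failures, all already randomized, and a psyllium share of 1/2, about 2.5, 5 or 7.5 would have taken psyllium. Section 12.6.1 starts evaluability at first FMP250, which these subjects never receive. They are therefore outside the toxicity population even if AE recording starts at consent.

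**5. The two starts side by side.** The consent-based paragraph of 13.4.1 covers days -3 to 0. The first sentence of 13.4.1 and Sections 12.6.1, 13.1 and 13.2 do not. The consent-based paragraph also speaks of reportable events. Under the definition in 13.1, an event in someone not yet given FMT is not, strictly, an AE. The consent-based start therefore needs the definitions changed to match it.

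**6. The causality rules side by side.**

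| Place | Causality is judged to |
|---|---|
| Section 13.4.2.2 | FMT |
| Section 13.1.11 | study treatment (undefined) |
| Section 13.4.1, case report form | study product (undefined) |

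Section 13.4.2.2 classes an event as not related to FMT when another factor, such as a concomitant treatment, explains it better. Followed literally, an event best explained by psyllium is coded not related. Under 13.1.11 the same event could be coded definite. No passage asks for a separate judgement on psyllium.

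**The case against.** A reader might infer that psyllium harms before day 0 go uncollected. The documents do not support that. Section 13.4.1 records from "any time after informed consent is obtained", documents all AEs whatever their cause, and has the investigator ask at each visit about events since the last one; subjects attend in person on day 0. Section 13.1.12 likewise records all AEs regardless of relation to FMT, and Section 4.5 keeps SAEs for screen failures. These points stand. What remains is a conflict over which start governs. It is not academic: the day-0 procedure list in Section 6.1.2.1 has no AE evaluation, while the lists for weeks 4, 8 and 12 do.

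A reader might also infer that no event is ever attributed to psyllium. That too goes beyond the text. *Study treatment* and *study product* could include psyllium, which is described in Section 7 under study intervention. They are not defined to do so, however, and Section 13.4.2.2, which sets the detailed rules, speaks only of FMT.

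Nor does Table 1 show AE evaluation starting later than psyllium. As read here, both rows appear to begin at day 0, and column positions in the extracted table are uncertain.

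The strongest defence is that psyllium safety does not hinge on individual causality judgements. The randomized comparison of placebo FMT with fiber against placebo FMT alone in Section 12.1 can use all events. This stands for all-cause counts. It does not rescue the treatment-related count in Section 12.4.2, and that comparison has only 22 or 23 subjects per group.

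Finally, assessors are blinded and no placebo powder is described. A psyllium causality question could prompt them to find out who took it. That is a real cost, and the fix must deal with it.

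**Conclusion.** The concern holds as an inconsistency with three parts.

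- **Start point.** If the FMT-anchored wording governs, 5.1% of the psyllium course (201 to 204 subject-days in 67 or 68 subjects) precedes monitoring. If the consent-based wording governs, none does. This assumes 45 per arm and an even split of Group 3.
- **Population.** Psyllium-exposed subjects who fail on day 0 are outside the toxicity population under either start, with only SAEs listed among the data kept for them. Their number is not stated; 2.5 to 7.5 is illustrative and rests on the assumed 5 to 15 day-0 failures.
- **Causality.** Section 13.4.2.2 conflicts with Sections 13.1.11 and 13.4.1, and its literal rule would misclassify psyllium events in the treatment-related AE count throughout the 59 days. How many events this affects cannot be estimated from the documents.

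No design figure changes, and most psyllium exposure is monitored in any case. The point should be corrected because the plan claims to inform on fiber safety and the correction is cheap.

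**What to change.** 1. Align the first sentence of 13.4.1, the definitions in 13.1 and 13.2, and Section 12.6.1 with the consent-based start already in 13.4.1. Add an AE evaluation to the day-0 procedures so that this start is carried out.
2. Define the safety population as everyone who took any psyllium or any FMP250, investigational or placebo. Extend the minimum data in Section 4.5 to all AEs for screen failures who took psyllium.
3. Reconcile 13.4.2.2 with 13.1.11 and the case report form wording in 13.4.1 so that causality covers all study interventions, and define *study treatment* and *study product*. State which relatedness judgement feeds the treatment-related count in Section 12.4.2.
4. Record psyllium relatedness separately without revealing allocation to the blinded assessor, for example by asking the same question for every subject regardless of arm.

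**Cost:** protocol wording, one additional form field, and a small blinding risk to manage. Sample size and the primary analysis are unaffected.

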2.5 Risk/Benefit Assessment

2.5.1 Known Potential Risks

2.5.1.1. FMT-related: (adapted from OpenBiome FMP250 Investigator Brochure V4.0):

The following adverse reactions have been reported in scientific literature to be commonly caused by FMT material within 24 hours post-procedure:

- Transient diarrhea, abdominal cramps/discomfort, and nausea
- Fever, bloating, belching, vomiting, borborygmi
- Constipation and flatulence
- Flares in IBD patients

These symptoms are usually self-limiting and of short duration. They may also be attributable to the delivery modality (e.g. colonoscopy or upper endoscopy) or underlying disease.

According to Openbiome and/or peer-reviewed literature, the following serious adverse events are potential risks that have been observed by FMT-based products (not specifically Openbiome) or included based on biological plausibility:

1. Infection
 - a. Bacterial infections from multi-drug resistant organisms (MDROs) (i.e. extended spectrum beta-lactamase (ESBL)-producing Enterobacteriaceae, vancomycin-resistant enterococci (VRE), carbapenem-resistant Enterobacteriaceae (CRE), and methicillin-resistant *Staphylococcus aureus* (MRSA))
 - b. Shiga Toxin-Producing *E. Coli* (STEC) Infections
 - c. Enteropathogenic *E. Coli* (EPEC) Infections
 - d. SARS-CoV-2 Infection
 - e. Diverticulitis, bacteremia, cytomegalovirus colitis, fever, diarrhea, encephalophagy and pancytopenia, Influenza B and diarrhea, norovirus gastroenteritis
 - f. Monkeypox Infection
2. Aspiration from upper GI delivery of FMT
3. GI complications (i.e. diarrhea, abdominal pain, appendicitis, peritonitis, IBD flare, and diverticulitis)
4. Allergy/Anaphylaxis
5. Autoimmune disorders
 - a. Exacerbation of pre-existing autoimmune conditions
 - b. Development of Rheumatoid arthritis, Sjogren's disease, peripheral neuropathy, idiopathic thrombocytopenic purpura
6. Non-infectious disease transmission (i.e. obesity, metabolic syndrome, cardiovascular disease, neurologic disorders, psychiatric conditions and malignancy)

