2.5.1.2. Psyllium-related

The FDA {CFR - Code of Federal Regulations Title 21} recommends sufficient liquid consumption when taking dried psyllium husk to avoid any potential risk for choking. In geriatric patients, some rare side effects may include abdominal discomfort, nausea, mild abdominal cramps, griping, and faintness³⁴. Additionally, our investigators hypothesize that bloating could occur as a side effect.

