Similar analyses will be conducted for secondary and exploratory endpoints (i.e., need for escalation, clinical remission, etc.). For secondary efficacy and safety analysis, comparison populations include: (i) FMT alone (no fiber) vs. placebo FMT alone (no fiber); (ii) FMT (with or without fiber) vs. placebo FMT (with or without fiber); (iii) placebo FMT with fiber vs. placebo FMT alone (no fiber); (iv) FMT with fiber vs. placebo FMT with fiber. All p-values will be two-sided with statistical significance evaluated at the 0.05 alpha level. Ninety-five percent confidence intervals for all parameters of interest will be calculated to assess the precision of the obtained estimates. Secondary analysis excluding subjects who discontinued the study treatment for reasons clearly not related to the study medications will also be performed. Treatment groups will be assessed at baseline with primary objective criteria. Balance between treatment groups will be assessed by ANOVA tests or Kruskal-Wallis tests for continuous variables and chi-square tests or Fisher’s exact tests for categorical variables.

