12.4.2 Analysis of Secondary Endpoints

- a. Clinical remission at week 8 post-FMT, as defined by Mayo score ≤ 2 without any sub-score >1
- b. Endoscopic response or remission, as defined as a Mayo endoscopic sub-score 0-1 with at least a 1-point reduction from baseline or a Mayo endoscopic sub-score of 0
- c. Safety will be assessed by:
 1. Subject mucosal biopsies, stool and blood testing.
 2. Subject symptomatology via medical interview, physical exam, and Mayo score and change in standard UC medications.
 3. Number and type of treatment related adverse events
 4. Number and type of disease-related complications such as hospitalizations, surgeries and endoscopies, medical complications, and mortality.

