13.1.1 Investigational Drug, FMP250, Risks (Potential Adverse Events)

There may be risks for this therapeutic intervention which will be discussed with study participant by the research doctor. Risks from donor stool, such as serious blood-stream infection (rare) or fevers, abdominal cramping, bloating, diarrhea, and bloody stool (less likely). The potential risks associated with FMP250 may include but are not limited to the following:

- Transmission of infectious organisms (bacterial, viral, fungal) contained in the stool
 - Multi-Drug Resistant Organisms (MDROs)
 - A potential risk of fecal microbiota transplantation (FMT) is the transmission of antibiotic-resistant bacteria. These are bacteria that are resistant to some antibiotics. These bacteria could be transmitted through FMT and could cause serious infection or death.
 - The study drug, FMP250, that will be delivered by FMT is provided by OpenBiome, a universal stool bank where donors who provide stool for FMT undergo regular screening for certain antibiotic-resistant bacteria. Each FMT is only made available when these screens do not detect antibiotic-resistant bacteria in the donor before and after the stool donation. Donors also undergo regular clinical assessments for any risk factors associated with carrying antibiotic-resistant bacteria, such as recent use of antibiotics, visiting certain healthcare facilities, or certain travel activities.
 - Shiga Toxin-Producing E. Coli (STEC) and Enteropathogenic E. Coli (EPEC)
 - A potential risk of fecal microbiota transplantation (FMT) is the transmission of STEC and EPEC. STEC is a type of E. coli that can produce a toxin called Shiga toxin. Shiga toxin can be transmitted through FMT and can cause symptoms like abdominal pain, diarrhea (often bloody), vomiting, and mild fever. Most people develop symptoms within 3-4 days of acquiring the bacteria, and most get better within 5-7 days. EPEC is another type of E. coli that can be transmitted through FMT and is generally carried asymptotically but can sometimes cause transient watery diarrhea, similar to traveler's diarrhea. Symptoms typically resolve in a matter of days.

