13.1.7 Risk from Psyllium Husk (Potential Adverse Events)

The main concern with psyllium husk is the risk of choking, specifically if the product is not consumed with sufficient liquid. Our research physicians also hypothesize bloating may occur. The following rare side effects may be of concern for older adults: abdominal discomfort, nausea, mild abdominal cramps, griping, and faintness.

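### Bloating, which the investigators predict for psyllium and list as an FMT reaction, is not among the nine solicited adverse events, so mild bloating may be under-counted or reported differently by arm

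*Combined protocol and SAP*

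**What the plan says.** All references are to the combined protocol and SAP.

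- **Solicited events (13.4.1).** "The following AEs will be solicited via phone calls and clinic visits by a study coordinator, along with the intensity of each". The list is fever, chills, fatigue/malaise, anorexia, abdominal pain, constipation, diarrhea, nausea and vomiting, each with severity wording.
- **Psyllium (2.5.1.2 and 13.1.7).** "our investigators hypothesize that bloating could occur as a side effect", and again "Our research physicians also hypothesize bloating may occur". Section 13.1.7 also says "The main concern with psyllium husk is the risk of choking" and adds rare effects in older adults.
- **FMT (2.5.1.1 and 13.1.1).** Reactions commonly reported within 24 hours include "Fever, bloating, belching, vomiting, borborygmi". Bloating appears again among the donor-stool risks.
- **Other routes to the record (13.4.1).** There is a general question on how the subject has been feeling, diary review, examination, investigator inquiry at each visit, and an instruction to contact the physician about symptoms. Any AE that is reported must be recorded whatever its severity (13.1.12).
- **Use of the data.** Safety is assessed partly by "Number and type of treatment related adverse events" (12.4.2). Section 12.1 lists safety comparison populations, including "placebo FMT with fiber vs. placebo FMT alone (no fiber".

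**The concern.** A symptom that is asked about by name, with a fixed grading, is collected in the same way from everyone. A symptom left to an open question depends on what the subject chooses to mention. Bloating falls in the second group, although the protocol expects it from both interventions.

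Two things could follow. Mild bloating may be under-counted in all arms. Reporting may also differ by arm: psyllium is handed out in the maker's labelled bottle (6.1.2, 7.4.4), no placebo fiber is described, and anticipated AEs are disclosed at consent (13.1.15). Subjects therefore know whether they take fiber and may know what to expect from it. In addition, the study coordinator who solicits AEs has access to the randomization list (7.12).

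At stake is the mild-tolerability part of the safety comparison between fiber and no fiber, in a trial whose main question is whether to add fiber to FMT.

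**Working it through.** **1. Is bloating prompted?** The 13.4.1 list has nine items and bloating is absent. The nearest item, abdominal pain, is graded by pain, so painless distension does not fit it. The other named follow-up topics are stool form and frequency, fever and subjective well-being.

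**2. Expected symptoms against prompted symptoms.** Cramps, discomfort and griping are counted here as prompted under abdominal pain.

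| Source | Symptoms named | Prompted | Not prompted |
|---|---|---|---|
| FMT, 2.5.1.1 (IBD flare left out) | 10 | 6: diarrhea, cramps/discomfort, nausea, fever, vomiting, constipation | 4: bloating, belching, borborygmi, flatulence |
| Psyllium, 13.1.7 | 7 | 4: nausea, discomfort, cramps, griping | 3: choking, bloating, faintness |

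Bloating is the only symptom in both right-hand cells.

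**3. How many subjects take psyllium?** All 45 in the FMT + psyllium arm and half of the 45 in the placebo arm (3.1): 45 + 22 or 23 = 67 or 68 of 135.

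**4. What could unprompted capture do?** The plan gives no figure to reproduce. The rates below are assumptions, chosen only to show the mechanism. Observed rate = true rate × share of cases captured, with the true rate set at 30% with and without fiber.

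| Share captured, fiber / no fiber | Observed, fiber | Observed, no fiber | Apparent risk ratio |
|---|---|---|---|
| 50% / 50% | 0.30 × 0.50 = 15% | 15% | 1.0 |
| 60% / 40% | 0.30 × 0.60 = 18% | 0.30 × 0.40 = 12% | 18/12 = 1.5 |
| 80% / 40% | 0.30 × 0.80 = 24% | 12% | 24/12 = 2.0 |
| 40% / 60% | 12% | 18% | 12/18 = 0.67 |

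Equal capture loses events without biasing the comparison. Unequal capture can create a difference in either direction where none exists.

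**5. Could a bloating comparison be tested?** The table shows the fiber-group rate needed for 80% power with the uncorrected two-sided 0.05 chi-square test, by exact enumeration. The control rates are assumptions.

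| Control rate | Placebo FMT with v without fiber, 22 v 23 | FMT + psyllium v FMT alone, 45 v 45 |
|---|---|---|
| 5% | about 37% | about 25% |
| 10% | about 46% | about 33% |
| 20% | about 60% | about 47% |

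Only large differences would be detected, so bloating counts should be reported descriptively.

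**The case against.** The strongest reply is that little of consequence can be missed. Section 7.10 covers a subject who cannot tolerate the fiber: reduce to one teaspoon a day for a week before stopping. Section 8.1 requires the reason for discontinuation, and 13.4.1 requires actions taken because of an AE to be recorded. Bloating bad enough to change dosing therefore has its own route. A coordinator asking about abdominal pain or well-being may also hear about bloating, and consent has already alerted subjects to it. Section 15 lets any study team member record AEs, which softens the point about the coordinator's list access. Choking and faintness are unprompted too, so singling out bloating is partly a choice, and it rests on how abdominal symptoms are classified. Finally, asking everyone does not hide fiber status, so expectation bias would remain.

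Most of this stands, and it limits the point to mild bloating that changes nothing in dosing. It does not remove the point. The recording rules act only after bloating has surfaced, and what is missing is a standard prompt and grade. Choking and faintness are on the psyllium list only, and faintness is tied to older adults. Bloating is on both lists, and the psyllium sections attach no age limit to it.

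A reader might infer that bloating goes unrecorded altogether, or that the gap inflates bloating in the fiber groups. The documents support neither: every reported AE must be recorded, and nothing in them fixes the direction of any reporting difference.

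**Conclusion.** The omission is real and the consequence is modest. Mild bloating that does not alter dosing is captured only if it happens to surface, so its counts may be too low or not comparable between fiber and no-fiber subjects. No size or direction can be given; the risk ratios above rest on assumed rates. The arm-difference part assumes that subjects know their fiber status, which follows from labelled bottles and the absence of any described placebo fiber.

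It would be a mistake to read this as a threat to the primary result or to the detection of serious harm. The primary endpoint is Mayo-based clinical response at week 8, and serious events have their own definitions and reporting rules in Section 13. This is a low-cost improvement to consider.

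**What to change.** Add bloating/abdominal distension as a tenth solicited event in 13.4.1. Use the mild/moderate/severe wording already given for chills and one scripted question, identical in all arms.

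**When.** Ask once at screening, before psyllium is handed out, then at every contact already in 13.4.1: day 1 and weeks 2, 4, 6, 8, 10 and 12. At week 8, ask before the sigmoidoscopy. Continuing to week 12 keeps the item on the same schedule as the other nine and covers the placebo arm after its investigational FMT at week 8.

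**Reporting.** Describe by arm, with the placebo arm split by fiber and without a test:
- baseline
- day 1 separately, because bowel preparation and colonoscopy gas affect every arm (7.8.1, 13.1.10)
- worst grade over weeks 2 to 8
- weeks 10 to 12 separately, because the placebo arm has by then received investigational FMT

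**Cost.** There are 1 + 7 = 8 short answers per subject, so 8 × 135 = 1,080. If all 150 screened subjects answer the baseline question, the total is 150 + 7 × 135 = 1,095. No new visit, test or staff is needed. The downsides are slightly longer contacts, more mild events on file, and residual expectation bias in subjects who know they take psyllium.
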